5.2 Use of co-intervention (if applicable)

Not applicable.

5.3 Escape medication (if applicable)

Not applicable.

6. INVESTIGATIONAL PRODUCT

Not applicable.

7. NON-INVESTIGATIONAL PRODUCT

Not applicable.

8. METHODS

8.1 Study parameters/endpoints

8.1.1 Main study parameter/endpoint

The first primary outcome is postoperative complications as measured by the Comprehensive Complication Index score, a combined outcome measure of morbidity and mortality.⁷⁸

The second primary/confirmatory outcome is the patients' functional capacity 8 weeks postoperatively, as measured by the six-minute walk test (6MWT).

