Main study parameters/endpoints: The primary endpoints are functional capacity, measured by the 6-minute walk test (6-MWT) and postoperative complications expressed by the Comprehensive Complication Index (CCI). Secondary outcomes include Patient Reported Outcome Measurements (PROMs) such as health related quality of life (HRQoL) (EORTC QLQ-CR29 and EORTC QLQ-C30, RAND questionnaires) and depression and anxiety scores (GAD-7, PHQ-9 questionnaires), functional capacity (VO₂max, sit to stand test, stair climb test, hand grip strength and activity questionnaire), nutritional status, length of hospital stay, study compliance, patient satisfaction and a cost-effectiveness analysis.

Nature and extent of the burden and risks associated with participation, benefit and group relatedness: Side effects might be cardiac arrhythmias or other exercise related problems during the VO₂ maximal intensity exercise tests. Exercise training is not expected to cause any risk to patients. However, since patients are thoroughly screened, we expect to find more pre-existing cardio-pulmonary conditions, for which patients will be referred to either a pulmonologist or cardiologist. The amount of tests might be perceived as a burden for the patients in both groups, as well as the amount of hospital visits for the prehabilitation group.

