4.4 Sample size calculation

The sample size calculation is based on the primary aim, to lower postoperative complications as determined according to the CCI score. With our population variables, CCI mean is 10.4 (SD 14), aiming to see decrease of 30%. We use an alpha of 0.05 and power of 0.80 (two-sided test). 10% dropouts are expected. We than need 708 patients, 354 per arm. This gives us a 100% efficacy to see a 6MWT proportion of improvement difference (55% versus 20%) as observed in previous studies.^{7,8} Each year around 800 eligible CRC patients undergo surgery in the participating hospitals in total, indicating that we will finish inclusion within 2 year time, with subsequent follow-up of 1 year.

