9.9 Interim analysis (if applicable)

Due to limited clinical data and resulting uncertainty regarding effect size of the primary endpoint – CCI - an interim analysis will be performed. The interim analysis is planned if half of the intended number of subjects have completed the 8 week assessment (i.e. timing of the primary endpoint assessment). The intention of the interim analysis is to terminate the study if there is a statistical significant difference between study arms at an alpha of 0.0054 (O'Brien-Fleming stopping rule) or if the recalculated sample size is deemed unattainable (i.e. larger than 1000 patients) or if the difference is not clinically relevant (<5 percent)

The sample size at the time of interim analysis will be sufficient to still show clinically relevant statistical differences regarding the second primary endpoint (i.e. 6MWT).

The interim analysis will be performed by the epidemiologist of the MMC, who is not a member of the DSMB. Early termination of the study will be decided upon by the DSMB.

To account for the alpha spending upon interim analysis (the final alpha will be 0.049), the sample size needs a minor adjustment from 708 to 713 patients. If the sample size recalculation in the interim analysis implies adjustment of the required sample size, this will be processed through an amendment to the protocol.

10. ETHICAL CONSIDERATIONS**10.1 Regulation statement**

The study will be conducted according to the principles of the Declaration of Helsinki⁵⁵ and in accordance with the Medical Research Involving Human Subjects Act (WMO).

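### Two primary endpoints, but no significance level for 6MWT and no rule linking its test to the CCI test: a false primary claim has about a 9-10% chance if 6MWT is tested at 0.05 and either result counts

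*Protocol*

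**What the plan says.** The Summary treats the two endpoints as equals and lists 6MWT first: "The primary endpoints are functional capacity, measured by the 6-minute walk test (6-MWT) and postoperative complications" by CCI. Section 8.1.1 reverses the order. It says "The first primary outcome is postoperative complications as measured by the Comprehensive Complication Index score", and then: "The second primary/confirmatory outcome is the patients' functional capacity 8 weeks postoperatively, as measured by the six-minute walk test (6MWT").

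Section 9.6 gives each endpoint its own test. CCI gets a t-test, a Mann-Whitney test or a zero-inflated method. 6MWT gets a mixed model of the arms over time.

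Section 4.4 sizes the trial on CCI alone: "The sample size calculation is based on the primary aim, to lower postoperative complications as determined according to the CCI score". Its inputs are "CCI mean is 10.4 (SD 14), aiming to see decrease of 30" per cent and "We use an alpha of 0.05 and power of 0.80 (two-sided test"). For 6MWT it gives only a responder contrast (55% versus 20%) with power of 100%, and no level.

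Section 9.9 tests CCI at 0.0054 at the interim and 0.049 at the end, and raises the sample size from 708 to 713 for that look. The trial may stop for a significant CCI difference, for a recalculated sample size above 1000, or for a CCI difference below 5 percent. The protocol then says that the interim sample will be "sufficient to still show clinically relevant statistical differences regarding the second primary endpoint (i.e. 6MWT").

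**The concern.** When two endpoints are both primary, the plan must say either that both have to be significant, or how one alpha is shared or ordered between them. This protocol does neither. Yet it fixes alpha in detail for the interim look, which is the smaller source of multiplicity.

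The 6MWT sentence in section 9.9 makes the gap matter in practice. The trial may stop because the CCI difference is not relevant, and 6MWT is then still expected to show a difference. That fits neither a CCI-first sequence nor a both-required rule. A trial that has failed on CCI could then present 6MWT as a positive primary result at a level never set in advance.

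**Working it through.** **1. The plan's own sample size.** Inputs from section 4.4: mean 10.4, SD 14, 30% decrease, two-sided alpha 0.05, power 0.80, 10% dropout.
- Difference: 0.30 × 10.4 = 3.12.
- Normal approximation: n = 2 × (1.960 + 0.842)² × 14² / 3.12² = 316.1, so 317 per arm. The exact t-test needs 318.
- Dropout: 318 / 0.90 = 353.3, so 354 per arm and 708 in total. This matches the protocol, so the undivided 0.05 is used for CCI.

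**2. The adjustment to 713.** 708 × [(z(0.9755) + 0.842) / (1.960 + 0.842)]² = 712.4, so 713. The increase covers the interim look and nothing else.

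**3. Two primary tests.** Assumptions: neither endpoint differs between arms, 6MWT is tested at 0.05, and a win on either counts. The chance of at least one false claim is 1 − P(|Z1| < 1.96 and |Z2| < 1.96). With independent tests this is 1 − 0.95² = 9.75%. The protocol gives no correlation between the tests, so a range is shown:

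| Correlation | Both tests at 0.05 | CCI at 0.049, 6MWT at 0.05 |
|---|---|---|
| 0 | 9.75% | 9.65% |
| 0.3 | 9.51% | 9.42% |
| 0.5 | 9.07% | 8.99% |
| 0.7 | 8.35% | 8.27% |
| 0.9 | 7.04% | 6.97% |

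**4. Adding the interim look.** At half information the interim and final CCI statistics have correlation √0.5. With levels 0.0054 and 0.049, CCI alone has error 1 − P(|Z1| < z(0.9973) and |Z2| < z(0.9755)) = 5.11%. With an independent 6MWT test at 0.05 the total is 1 − (1 − 0.0511) × 0.95 = 9.85%. A simulation of 2 million trials gave 9.9%, 9.6% and 9.2% at correlations 0, 0.3 and 0.5.

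**5. What control would cost.**
- Equal split, 0.025 each: CCI needs 383 per arm, 426 with dropout, 852 in total. With 318 evaluable per arm, CCI power falls to 71.5%.
- 0.001 for 6MWT and 0.049 overall for CCI: solving the expression in step 4 for a total of 0.049, with 0.0054 at the interim, gives a final CCI level of 0.0468. With 318 per arm the expected statistic is 3.12 / (14 × √(2/318)) = 2.81. Power is 79.4% from the final test alone and 79.6% counting the interim look, so about 79.5%. Section 9.9's levels give 80.0% and 80.2% on the same two counts.
- 6MWT at 0.001 with half the evaluable patients (159 per arm), 55% versus 20%, pooled proportion 0.375: (0.35 − 3.29 × √(2 × 0.375 × 0.625 / 159)) / √((0.55 × 0.45 + 0.20 × 0.80) / 159) = 3.38, so power is 0.9996.

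**The case against.** The unnumbered paragraph above section 9.6 promises a detailed analysis plan before the final data freeze. That plan is not shown, and a testing order could be set there. There is also evidence of a ranking. CCI is the first primary, the sample size rests on it, sections 9.2.2 and 9.9 call it the primary endpoint in the singular, and the efficacy stop uses CCI only. Spending the whole alpha on CCI is also what a CCI-first sequence would do.

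Part of this stands. A reader might infer that the protocol tests both endpoints at the full level and so breaks a promised 5% overall error rate. The document does not support that reading. It states no level for 6MWT, it gives 0.05 as the design alpha for CCI and not as a rate across both endpoints, and it never says that either endpoint alone is enough. The 9-10% is therefore conditional.

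The labels still set no gate, the Summary puts 6MWT first, and the 6MWT sentence in section 9.9 works against a CCI-first reading. The trial can stop at the interim, before the analysis plan need exist, so the rule belongs in the protocol.

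A reader might also infer that control costs 6MWT nothing. The 0.9996 is for a comparison of two proportions, whereas section 9.6 plans a continuous mixed model. No 6MWT SD or mean difference is given, so the power of that test at 0.001 cannot be derived.

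**Conclusion.** The point holds as a gap in what the protocol itself fixes: two primaries with separate tests, all the alpha used for one, an adjustment for the interim only, and a second primary that survives a CCI stop for lack of relevance. As written, the error rate across the two primaries is not controlled.

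The 9-10% rests on three assumptions: 6MWT is tested at 0.05, a win on either endpoint counts, and the correlation is at most about 0.5. If both endpoints were required, or 6MWT were tested only after a significant CCI, there would be no inflation from the second endpoint, but neither rule is stated. Separately, the levels 0.0054 and 0.049 give CCI alone about 5.1%, slightly above 5%. This should be corrected before the interim.

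**What to change.** Add one rule to section 9.6 before the interim analysis:
- Test 6MWT at 8 weeks at 0.001, using the week-8 treatment contrast from the mixed model, so that the test matches the endpoint in section 8.1.1.
- Test CCI at 0.049 overall across interim and final. With 0.0054 at the interim, the final level is about 0.0468, replacing the 0.049 in section 9.9.
- Whichever endpoint is significant passes its alpha to the other.
- Apply the same rule if the trial stops at the interim. After a significant CCI, 6MWT is tested at 0.05 (0.001 + 0.049). After a stop for any other reason, it is tested at 0.001.

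Restate CCI power as about 79.5% with 318 evaluable per arm rather than enrolling more. Scaling as in step 2 of the working would otherwise need about 722 patients.

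The cost is one paragraph, a changed final level, about half a percentage point of CCI power, and a stricter level for 6MWT when CCI is negative.

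A fixed sequence, CCI first and then 6MWT, is simpler and keeps the CCI level whole. It is an option only if the sponsor accepts that a negative CCI bars any confirmatory 6MWT claim and amends the 6MWT sentence in section 9.9 to match. The final CCI level would still need correcting, because of the 5.1% in step 4.

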8.1.2 Secondary study parameters/endpoints (if applicable)

Secondary outcomes include Patient Reported Outcome Measurements (PROMs) such as health related quality of life (HRQoL) (EORTC QLQ-CR29 and EORTC QLQ-C30, RAND questionnaires) and depression and anxiety scores (GAD-7, PHQ-9 questionnaires), functional capacity (VO₂max, sit to stand test, stair climb test, 1-RM, hand grip strength and self-reported physical activity), nutritional status, length of hospital stay, study compliance, and a cost-effectiveness analysis.

8.1.3 Other study parameters (if applicable)

Surgery and anesthesia care

Surgery will be performed in all institutions by one of the three/four colorectal surgeons. Surgical approach, including laparoscopic or open surgery, stoma placement, etc will be at the discretion of the surgeon. Perioperative care will follow the Enhanced Recovery After Surgery (ERAS) program, which is an evidence-based multidisciplinary care plan.⁷⁹ The ERAS for colorectal surgery started to be operational since several years in all participating centers and regroups all the colorectal surgeries, and includes patient education, preoperative feeding, selected bowel preparation, laparoscopic approach, multimodal analgesia, maintenance of perioperative normothermia, early oral intake and early mobilization, early removal of catheters and drains, and a planned 3-5 day hospital stay.

We add chewing gum and coffee drinking to the current ERAS program, since they have both been investigated as beneficial improving recovery of patients bowel function.⁸⁰

8.2 Randomization, blinding and treatment allocation

Patients will be randomized by block randomization with a block size of 8, with a 1:1 allocation by means of randomization software, stratified by study sites, neoadjuvant therapy vs. no neoadjuvant therapy and tumour location (colon/rectum). Patients will be allocated either to the prehabilitation intervention group, receiving 4 weeks prehabilitation, or to the control group, receiving no prehabilitation (standard care). Both groups will receive 8-week rehabilitation following the current international ERAS guidelines. Similarly all the perioperative care will follow the ERAS guidelines for colorectal surgery.

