3. STUDY DESIGN

This is an international multicenter, randomized controlled trial with two randomized groups. Patients of adult (>18 years) age undergoing elective colorectal resection for cancer are eligible for inclusion. A total of 708 patients will be included in six participating centers (Copenhagen, Veldhoven, Montréal, Barcelona, Ferrara, Paris). Study will aim to start may of 2017 in Máxima Medical Center, Veldhoven, The Netherlands, and in Montréal General Hospital, Canada, and in 2017 in the other participating centers. Inclusion of patients will take approximately 2 years and the follow-up is 1 year.

The control group in this study will receive standard care according to international ERAS protocol.

An overview of the measurements during the PREHAB study can be found in appendix I. These measurements will be applied in the control group as well as the intervention group.

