9.6 Primary study parameter(s)

Data will be analyzed on an intention-to-treat basis. In addition, a per-protocol analysis will be performed.

The first primary outcome is postoperative complications, as scored by the Comprehensive Complication Index score (CCI).¹²⁵ Data will be collected as a continuous variable and calculated through the sum of morbidity and mortality presented on the Clavien Dindo classification.¹²⁶ CCI score will be calculated at the 30 day follow up.

CCI will be described as mean plus standard deviation (SD). However since we expect CCI to be right skewed (i.e. tail to the right) we will also describe CCI as median plus interquartile range (IQR) and percentage above 20.

We will visually check the distribution of the CCI data using histograms and calculating skewness and kurtosis. If necessary and if possible the data will be normalized by applying (normal) logarithmic transformation.

To test the hypothesis (H0) that the study arms result in similar CCI's (i.e. prehabilitation does not prevent postoperative complications), we will use the student T-test if data follow a normal distribution, a Mann-Whitney U if data do not follow a normal distribution or statistical methods that take into account a possible zero-inflated nature of the data.

The second primary/confirmatory outcome is the patients' functional capacity, as measured by the six-minute walk test (6MWT). The 6MWT is a continuous variable and calculated at baseline (inclusion to the study), a few days before surgery and 4 and 8 weeks after surgery.

Data will be described by means plus SD per time point. To accommodate the repeated measurements within individuals we will use a generalized linear mixed model to statistically test the hypothesis of both study arms being equal regarding functional capacity over time.

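### Two of the three CCI tests named in section 9.6 cannot use the randomisation strata; if the strata predict CCI, this forgoes a little power

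*Protocol*

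**What the plan says.** Section 8.2 of the protocol specifies "block randomization with a block size of 8, with a 1:1 allocation by means of randomization software", and the allocation is "stratified by study sites, neoadjuvant therapy vs. no neoadjuvant therapy and tumour location (colon/rectum"). Section 3 states that "A total of 708 patients will be included in six participating centers". Six sites, two neoadjuvant categories and two tumour locations give 6 × 2 × 2 = 24 nominal strata.

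For the CCI comparison, section 9.6 states that "we will use the student T-test if data follow a normal distribution". It names a Mann-Whitney U test if they do not, and as a third possibility methods suited to an excess of zeros, without naming a model. The stratification factors appear nowhere in 9.6, in 9.7 or in the interim analysis of 9.9.

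For the six-minute walk test (6MWT), 9.6 names a generalized linear mixed model for the repeated measurements and lists no fixed effects. The paragraph that opens the statistical analysis, just before 9.6, defers detail to a separate analysis plan, which is not at hand.

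**The concern.** Blocked randomisation within strata makes the arms nearly equal on the strata, so the true sampling variance of the difference in means no longer contains the between-stratum part of the outcome variance. A t-test or Mann-Whitney U still counts that part as noise. Where the strata are prognostic, the standard error is too large, the test rejects less often than its nominal level under the null, and part of the precision bought by stratifying is not used.

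The protocol gives some reason to expect a relation with CCI. Section 8.3 says that the Clavien-Dindo classification, on which CCI is built, correlates with the complexity of the operation, and tumour location plausibly bears on complexity. Section 8.1.3 leaves the surgical approach to the surgeon, and the centres are in six cities in different countries. How strong the relation is, the protocol does not say.

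The mention of a later analysis plan does not remove the point for CCI. Section 9.6 goes beyond silence: it names two tests that cannot include the factors, so an adjusted analysis in the analysis plan would depart from them.

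**Working it through.** **Inputs.** From section 4.4: "CCI mean is 10.4 (SD 14), aiming to see decrease of 30" per cent; "We use an alpha of 0.05 and power of 0.80 (two-sided test"); "10% dropouts are expected"; "We than need 708 patients, 354 per arm". The target difference is 0.30 × 10.4 = 3.12 points. The share of CCI variance explained by the strata, R², is not in the document. It is assumed to be 0.02 to 0.10, with 0 and 0.20 shown as limits.

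**The plan's own figure.** A two-sample t-test with difference 3.12, SD 14, two-sided alpha 0.05 and power 0.80 needs 317.03, that is 318 per arm. Then 318 / 0.9 = 353.3, that is 354 per arm, or 708 in total. This matches the stated number, so the sample size was set for an unadjusted comparison.

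**Effect of leaving out the strata, with n = 318 analysed per arm.** The standard error that the unadjusted test uses is SD × √(2/n) = 14 × √(2/318) = 1.110. The true standard error under stratified blocks is this times √(1 − R²). The standardised effect is θ = 3.12 / 1.110 = 2.810.

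- Actual alpha, unadjusted: 2 × [1 − Φ(1.96 / √(1 − R²))]
- Power, unadjusted: Φ((θ − 1.96) / √(1 − R²))
- Power, adjusted: Φ(θ / √(1 − R²) − 1.96)

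| R² (assumed) | Actual alpha, unadjusted | Power, unadjusted | Power, adjusted | Gain (points) |
|---|---|---|---|---|
| 0 | 0.050 | 80.2% | 80.2% | 0 |
| 0.02 | 0.048 | 80.5% | 81.0% | 0.5 |
| 0.05 | 0.044 | 80.8% | 82.2% | 1.4 |
| 0.10 | 0.039 | 81.5% | 84.2% | 2.7 |
| 0.20 (beyond the range) | 0.028 | 82.9% | 88.1% | 5.2 |

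Gains are taken before rounding. The right comparator for adjusted power is the unadjusted power in the same row, not the planned 80%, because stratified allocation raises the unadjusted test's power too. Expressed as sample size, 80% power with adjustment would need about 690, 670 or 634 patients including dropout at R² of 0.02, 0.05 or 0.10. With the final alpha of 0.049 from section 9.9 the gains hardly change: 0.5, 1.4 and 2.7 points.

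**Simulation check.** The simulation used 24 strata of assumed unequal sizes, blocks of 8, 636 patients analysed, a normal outcome and 4,000 runs per setting. The Monte Carlo standard error near 0.05 is √(0.05 × 0.95 / 4000) = 0.003.

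| R² | Null rejection: t-test | Mann-Whitney U | adjusted | Power: t-test | adjusted |
|---|---|---|---|---|---|
| 0.02 | 0.051 | 0.050 | 0.054 | 79.3% | 79.6% |
| 0.05 | 0.044 | 0.047 | 0.051 | 80.0% | 81.0% |
| 0.10 | 0.037 | 0.039 | 0.045 | 80.2% | 82.6% |

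At R² of 0.05 and 0.10 the direction and approximate size agree with the formulas, with slightly smaller power gains. At 0.02 the effect is too small to see. The simulated outcome is normal, so the simulation does not show what happens with a zero-heavy CCI.

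**The case against.** The strongest reply is that nothing planned is lost. The 708 was computed for an unadjusted test, that test still delivers about 80%, and its error rate is at or below 5%. This stands: what is forgone is power above plan.

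A second reply is that the size is unknown. Section 8.2 gives no reason for its choice of strata, and section 8.1.3 places all centres under the same ERAS care programme, which may limit differences between sites. This also stands, and it is why the result is conditional on R². At R² = 0 there is no effect.

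A third reply is that 9.6 leaves open a zero-inflated method, which in regression form could include the strata. Since 9.6 itself expects a right-skewed CCI, this route is a realistic candidate. That limits the point to two of the three routes.

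Two stronger readings are tempting. A reader might infer that the 6MWT analysis ignores the strata as well. The text does not support this: a mixed model can include them, 9.6 lists no fixed effects either way, and a covariate list may properly be left to the analysis plan. On the protocol's own 55% versus 20% improvement, power for 6MWT with 318 per arm is in any case practically 100%. A reader might also infer that the interim rule in 9.9, which allows stopping if the recalculated sample size exceeds 1000, would be triggered too easily by an unadjusted variance. Section 9.9 does not say which variance the recalculation uses, so this cannot be concluded.

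**Conclusion.** The point holds for CCI, on the t-test and Mann-Whitney routes, as a modest and free improvement. If the strata explain 2% to 10% of CCI variance, the unadjusted test runs at an actual alpha of 0.048 to 0.039 and gives up about 0.5 to 2.7 points of power against an adjusted test. These figures assume near-balance within strata and a normal approximation, and the variance share is an assumption without a source in the protocol. The trial's validity is not in question: type I error is not inflated and the planned power is not undercut by leaving out the strata. The 6MWT model is not part of the finding.

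**What to change.** In section 9.6, replace the unadjusted CCI test with a regression of CCI (transformed if the distribution check calls for it) on arm plus site, neoadjuvant therapy and tumour location as main effects. State that any zero-inflated model will include the same three factors. Main effects avoid fitting 24 cells, which would average 708 / 24 = 29.5 patients even if they were of equal size.

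If a rank test is kept, use a van Elteren test in place of the Mann-Whitney U. It compares arms within strata and cannot adjust for main effects, so sparse cells among the 24 have to be pooled by a rule written down beforehand, for example by collapsing strata. Use the same adjusted test at the interim analysis in 9.9, and settle the wording before that analysis.

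The cost is a change of text, with the usual submission of an amendment under section 11.3. The three factors are needed for randomisation and so are already recorded. No extra patients or measurements are required.
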